12.5. ECG

Observed and change from baseline values will be summarized by visit and for the last on-treatment measurement using descriptive statistics.

A shift table from baseline to on-treatment visit, for overall ECG interpretation (normal, abnormal not clinically significant, abnormal clinically significant and missing) will be summarised with marginal totals, using counts and percentages.

A shift table from baseline to the maximum post baseline QTcF value will be summarized according to the categories specified in the table below. The maximum will be taken from all scheduled and unscheduled on-treatment values.

Parameter	Criteria
QTcF	< 450 msec ≥ 450 msec and < 480 msec* ≥ 480 msec and < 500 msec* ≥ 500 msec*
QTcF increase from baseline	< 30 msec ≥ 30 msec and < 60 msec* ≥ 60 msec*

* Values of PCI.

Observed and change from baseline values will be listed. The listing will identify the last on-treatment measurement and QTcF values of PCI (identified in the above table).

12.6. PHYSICAL EXAMINATION

Physical examination data will be listed.

12.7. EYE EXAMINATION

Observed and change from baseline values for 4 cataract gradings in LOCS III (nuclear opalescence, nuclear colour, cortical and posterior subcapsular cataracts) will be summarized by visit using descriptive statistics. The summary will be across both eyes (i.e., each subject will contribute 2 values if they have a left and right eye reading at the visit) and repeated for the worst change at each visit.

Subjects with at least one change in spherical equivalent of ≥ 0.75 diopters in either eye will be listed separately and will include all the subject's spherical equivalent data reported during the study.

Eye examination data will be listed. There will be 7 separate eye examination listings - refraction, BCVA, pinhole visual acuity, slit lamp examination, cataract grading,

tonometry and irido-corneal drainage angle assessment. Subjects who had their cataracts assessed at screening using a different grading system will have their data listed separately from the remaining subjects to facilitate a medical review of this data.

BCVA (LogMAR scale) values will be presented to 1 decimal place and spherical equivalent refraction error values will be presented to 2 decimal places.

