Safety analyses will be performed on the Safety Population, defined as all subjects who are randomized and receive at least one dose of study drug. Subjects will be analyzed by the treatment received.

Treatment-emergent adverse events (TEAEs) will be summarized by treatment group and by System Organ Class (SOC) and Preferred Term, in accordance with the MedDRA coding dictionary. The number of subjects reporting each AE preferred term will be tabulated for all TEAEs and separately for those considered as at least possibly related to study treatment by the Investigator. Number of subjects reporting serious adverse events (SAEs) and adverse events of special interest (AESI) will also be tabulated.

Observed values and changes from baseline in clinical laboratory tests, vital signs, ECG data and eye examination data will be summarized using descriptive statistics by treatment group and visit.

Plasma concentrations of REN001 will be summarized over time using descriptive statistics for Day 1, Week 12 and Week 24. These data will also be included in a population PK analysis.

LIST OF STUDY PERSONNEL

Sponsor

[REDACTED]

Reneo Pharma Ltd.
[name],
[name],
[name]
United Kingdom

[REDACTED]

[REDACTED]

Reneo Pharma Ltd.
[name],
[name],
[name]
United Kingdom

[REDACTED]

Chief Investigator

[REDACTED]

Massachusetts General Hospital
[name]
[name]

[REDACTED]

**Contract Research
Organization**

Orphan Reach Ltd.
[name],
[name],
[name],
[name]
United Kingdom

[contact]

Medical Monitor

[REDACTED]

Email: [contact]

**Serious Adverse Event
Reporting**

Bionical Emas
[name]
[name],
[name],
Hertfordshire
[name]
United Kingdom

Email: [contact]
[contact]
US [contact]

Statistician

ParamStat Limited

TABLE OF CONTENTS

LIST OF STUDY PERSONNEL..... 13

1 INTRODUCTION..... 22

1.1 Indication 22

1.2 Background..... 22

1.3 Study Rationale..... 22

1.4 Risk-Benefit Assessment 23

1.5 Dose Selection Rationale 25

2 STUDY OBJECTIVES..... 26

2.1 Primary Objective 26

2.2 Secondary Objectives 26

2.3 Safety Objectives 26

2.4 Pharmacokinetic Objectives 26

2.5 Exploratory Objectives 26

3 OVERALL DESIGN AND PLAN OF THE STUDY 27

3.1 Overview..... 27

3.2 Endpoints 29

 3.2.1 Primary Endpoint 29

 3.2.2 Secondary Endpoints 29

 3.2.3 Safety Endpoints 29

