8.6 Safety Analyses

No imputation will be used for handling missing data, with the exception of conservative approaches taken for missing adverse event information (e.g., intensity). Details of such conventions will be documented in the Statistical Analysis Plan (SAP).

Treatment-emergent adverse events will be summarized by treatment group and by SOC and Preferred Term, in accordance with the MedDRA coding dictionary. The number of subjects reporting each AE preferred term will be tabulated for all TEAEs and separately for those considered as at least possibly related to study treatment by the Investigator. Number of subjects reporting SAEs and AESI will also be tabulated.

Changes from baseline in laboratory parameters, vital signs and ECG data will be summarized by treatment group and by visit. Baseline will be taken as the last measurement prior to dosing.

A categorical shift table of change from baseline will be summarized by treatment group and by visit for the eye examination parameters.

The incidence of potentially clinically significant laboratory and ECG values (e.g., increase in QTcF ≥ 30 msec from baseline or an absolute QTcF value of ≥ 500 msec) will be flagged in listings and summarized by treatment group.

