	
 • Section 10.3.9 6 Minute Walk Distance – clarified analysis model. • Section 10.4 Relationship of Endpoints – updated the secondary endpoint. • Section 12.1 Adverse Events – added a summary of lower-level terms for the AESI of refraction disorders. • Section 12.5 ECG – Added a shift table from baseline to the maximum post baseline QTcF. • Section 14 Changes from Planned Analyses Specified in the Protocol – documented the change in secondary endpoints, the change to the while on treatment analysis for the primary endpoint, and the addition of the phenotypic description questions as exploratory endpoints. 
Other minor clarifications and typographical errors have also been corrected.

3.0 (16Nov2023)
	
 • Section 4.2 Patient-Reported Outcomes Measurement Information System (PROMIS) Short Form – updated method for deriving T-score. • Section 4.5 and 10.3.2 Pedometer Step Count – added median daily step count endpoint and removed the exclusion of extreme values from the calculation of the endpoints. • Section 4.10 Work Productivity and Activity Impairment Questionnaire: Specific Health Problems – correction to calculation of Percent overall work impairment due to PMM formula. Clarified the calculation of percent overall work impairment due to PMM score when all the work time missed is due to PMM. • Section 6.7 and Section 12.7. Eye Examinations – updated the derivation for best corrected visual acuity (BCVA) to LogMAR scale and the reference used. Removed summaries of BCVA and spherical equivalence as this data is only considered as supportive information for the medical assessment of cataracts. • Section 7.5 Modified Full Analysis Set – updated definition to exclude late baseline visit data from on-treatment measurements. • Section 7.6 Per Protocol Analysis Set – added an additional criterion. • Section 7.8.2 Scan Analysis Set – clarified that the scan analysis set includes subjects that received at least one dose of study drug. • Section 8.2 General Methods – clarified precision to use for endpoints and any changes to the rule for precision is detailed in the relevant analysis sections. • Section 8.3.1 Efficacy Data – clarified intercurrent events where subjects still have ambulation but may be prevented from performing the test. Updated worst case imputation to clarify that the mean and standard deviation will be based on assessments where subjects

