3.2.3. Safety Endpoints

- Incidence and severity of adverse events (AEs)
- Absolute values, changes from Baseline and incidence of potentially clinically significant values for laboratory safety tests, electrocardiograms (ECGs), vital signs and eye assessments.

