6.7. EYE EXAMINATIONS

Eye examination data will be performed during the study by an appropriately qualified professional. Any abnormality considered clinically significant, will be reported as an AE.

Best corrected visual acuity (BCVA) can be assessed using the LogMAR scale, ETDRS letters or Snellen line. All results will be converted to the LogMAR scale before calculating changes from baseline at each visit for left and right eye BCVA (Roy 2003).

Where the Snellen scale has data recorded as x/y the MAR value is calculated by dividing y by x and then the LogMAR is the base 10 logarithm of the MAR value [i.e., $\text{LogMAR} = \log_{10}(\text{MAR})$]. Hence, higher scores indicate worse BCVA and increases from baseline indicate deterioration.

A change of 0.02 in LogMAR is equivalent to 1 letter. Hence, a Snellen scores with ‘-z’ or ‘+z’ indicating z letters fewer, or z letters more, respectively, will require an adjustment to the LogMAR score; 0.02 will be added or subtracted, respectively, for each letter (z).

e.g.,

$$20/15-1: \text{LogMAR} = \text{Log}_{10}(15 \text{ divided by } 20) + 0.02 = -0.105$$

$$20/15+1: \text{LogMAR} = \text{Log}_{10}(15 \text{ divided by } 20) - 0.02 = -0.145$$

If the Snellen scale is not reported in x/y format or x/y±z format, then the conversion to logMAR will not be done.

A change of 0.3 LogMAR (equivalent to 15 letters or 3-line change) is considered meaningful.

Refraction error based on spherical equivalent will be derived for each eye using the following formula:

$$\text{Spherical Equivalent (diopters)} = \text{cylinder (diopters)}/2 + \text{sphere (diopters)}$$

Changes from baseline at each visit will be calculated. A change ≥ 0.75 diopters will be reported as an AESI.

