Cataract are classified and graded against the Lens Opacity Classification System III (LOCS III) for nuclear opalescence, nuclear colour, cortical and posterior subcapsular cataracts. A change was made to the grading system used during the study. The original system was used at the screening visit for 30 subjects who were subsequently randomized. As the original data cannot be converted to the revised LOCS III grading system the data for these subjects (screening results recorded in the original format, and Week 12 and Week 24 results recorded in the new format) will only be listed and medically reviewed to identify any possible development of cataracts. Changes from baseline will be calculated for all other subjects. Higher scores equate to a deterioration in cataracts. The largest increase from baseline (or smallest decrease if both eyes show a reduction from baseline) across the eyes will be identified at each visit.

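### SAP 12.7 omits the by-arm eye shift table promised in Protocol 8.6 and only lists BCVA, so measured acuity change can be compared between arms only through reported AESIs

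*SAP*

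**What the plan says.** **Protocol.** The synopsis says that "eye examination data will be summarized using descriptive statistics by treatment group and visit". Section 8.6 adds a second output: "A categorical shift table of change from baseline will be summarized by treatment group and by visit for the eye examination parameters". Section 3.2.3 names eye assessments among the safety endpoints, and Section 7.1.1.5 makes changes in cataract or visual acuity an AESI.

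**SAP, endpoint and derivation.** Section 3.2.3 keeps the endpoint: "incidence of potentially clinically significant values for laboratory safety tests, electrocardiograms (ECGs), vital signs and eye assessments". Section 6.7 converts BCVA from LogMAR, ETDRS or Snellen readings to LogMAR, calculates changes for each eye and sets a threshold: "A change of 0.3 LogMAR (equivalent to 15 letters or 3-line change) is considered meaningful". It also derives spherical equivalent, with a change of 0.75 diopters or more reportable as an AESI.

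**SAP, analysis.** Section 12.7 gives descriptive statistics for the four LOCS III gradings (observed, change, and worst change across eyes). Everything else is listed. For refraction, "Subjects with at least one change in spherical equivalent of ≥ 0.75 diopters in either eye will be listed separately". For acuity, beyond the listing, the section sets only the number of decimals: "BCVA (LogMAR scale) values will be presented to 1 decimal place". The summary of changes for SAP version 3.0 gives the reason: "Removed summaries of BCVA and spherical equivalence as this data is only considered as supportive information for the medical assessment of cataracts".

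**The 30 subjects.** The cataract grading system changed during the study. SAP 6.7 states: "The original system was used at the screening visit for 30 subjects who were subsequently randomized". Their screening grades cannot be converted, so their cataract data are listed and medically reviewed, and no change from baseline is calculated.

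**The concern.** The SAP builds an acuity variable and a threshold for it, and then has no table that uses either. The protocol's categorical eye table is also absent, for LOCS III as well as for acuity and refraction. Eye assessments are thus the one group within the SAP 3.2.3 endpoint with no by-arm table of measured values against a criterion.

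What is at stake is a safety comparison on a risk the trial itself names. Without a table of measured BCVA, a difference between arms in three-line acuity loss would appear in a by-arm table only if the losses had been reported as adverse events. Otherwise it would have to be found by reading listings. A reader who relies on Section 14 for departures from the protocol would not learn that the shift table had gone.

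**Working it through.** No power or sample-size figure is involved. The check is mainly a comparison of sections, followed by two short calculations.

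**1. The four groups in SAP 3.2.3, side by side**

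| Group | By-arm table of measured values against a threshold or category |
|---|---|
| Laboratory (SAP 12.2) | Count of subjects meeting the listed criteria of potential clinical importance; shift tables |
| ECG (SAP 12.5) | Shift table to the maximum QTcF by category; shift table of overall interpretation |
| Vital signs (SAP 12.4) | Number and percentage by category of blood pressure change |
| Eye (SAP 12.7) | None. Descriptive statistics for LOCS III; listings for the rest |

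SAP 8.2 splits summary tables by treatment group, so the tables in the first three rows are by arm, and so is the LOCS III summary.

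**2. Do the AESI tables fill the gap?** SAP 12.1 tabulates AESIs by system organ class and preferred term, and refraction disorders also by lower-level term, which shows the direction of diopter change. For refraction this comes close to a threshold count, because Protocol 7.1.1.5 and SAP 6.7 fix the reporting trigger at 0.75 diopters. Acuity and cataract differ:
- Protocol 7.1.1.5 and 7.1.9 give no numeric trigger for BCVA. The 0.3 LogMAR figure appears only in the SAP, so nothing in the protocol obliges a site to report a three-line loss.
- Protocol 7.1.1.3 uses cataract as an example of a degenerative condition whose worsening is recorded as an event only when it exceeds what would be expected. That is a judgement by the investigator.

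**3. Is the departure recorded?** SAP Section 2 says that changes from the protocol's analyses will be identified in the SAP. Section 14, which lists them, has no eye entry. The version 3.0 change summary mentions the BCVA and spherical-equivalent summaries but not the shift table.

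**4. Size of the LOCS III loss.** Inputs: 30 subjects (SAP 6.7) and about 200 planned, allocated 1:1 (SAP 3.5 and 3.6).
- Share without a change from baseline: 30/200 = 15%, leaving about 170 (85%).
- Relative standard error of a difference in means: √[(1/n₁ + 1/n₂) / (1/100 + 1/100)].
- Even split of the 30 (85 and 85 remain): √(200/170) = 1.085, a rise of 8.5%.
- Split of 5 and 25 (95 and 75 remain): √[(1/95 + 1/75)/0.02] = 1.092, a rise of 9.2%.

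**5. The LogMAR figures.** The SAP's own values reproduce: 15 × 0.02 = 0.3; log₁₀(15/20) = −0.125, so one letter fewer gives −0.105 and one letter more gives −0.145. At one decimal both print as −0.1, although they differ by 0.04/0.02 = 2 letters.

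**The case against.** The sponsor's case is reasonable. The risk described in Protocol 1.4 is cataract formation. LOCS III measures it directly and keeps its by-arm summary. BCVA comes from mixed charts, and Snellen entries in other formats are not converted, so a summary would be imperfect. The reason for removal is written in the SAP, and Protocol Section 8 leaves details of presentation to the SAP. This supports treating BCVA as secondary evidence. It does not explain the missing shift table, which is absent for LOCS III too. It also sits awkwardly with an AESI definition that names visual acuity alongside cataract.

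Several stronger readings are tempting, and the documents do not support them:
- *The arms cannot be compared on cataract or vision.* They can: through LOCS III for about 85% of planned subjects, and through AESIs for the whole safety set, which includes the 30.
- *Refraction has no by-arm summary at all.* Refraction-disorder AESIs are tabulated by arm with direction.
- *The 30 are only listed, or BCVA and refraction are their only other measures.* They are also medically reviewed, and slit lamp and pinhole acuity data are listed for all subjects.
- *The 0.75-diopter rule would drop decreases because change is signed.* Protocol 7.1.1.5 does not limit direction, and SAP 12.1 captures it.
- *One-decimal rounding defeats the 0.3 criterion.* The rule affects how a listing is displayed; no planned derivation or table uses rounded values.

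**Conclusion.** The point holds as a gap in the safety tables and in the record of departures. Protocol 8.6's by-arm, by-visit categorical eye table is not in the SAP, measured BCVA is only listed, and the SAP's 0.3 LogMAR criterion feeds no table. The eye part of the SAP 3.2.3 endpoint therefore has no by-arm incidence table of measured values, and Section 14 does not say so.

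The size is moderate. For acuity, comparison between arms depends on investigator reporting without a numeric trigger. For cataract grade, the 30 unconvertible screening results cost about 8.5% to 9.2% in the standard error of a between-arm difference, which is lost precision and not a lost comparison. For refraction, the AESI table covers much of the need.

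These figures assume about 200 randomized at 100 per arm, complete LOCS III data in everyone else, and a split of the 30 between 5/25 and 25/5. The documents give neither the split nor the final number.

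**What to change.** In SAP 12.7:
1. Add a table by arm, at Weeks 12 and 24 and for the worst post-baseline value, giving the number and percentage of subjects with BCVA worsening of at least 0.3 LogMAR in either eye. Include everyone with convertible BCVA, the 30 among them.
2. In the same table, give the number and percentage with a spherical-equivalent change of at least 0.75 D, increases and decreases separately.
3. Add a LOCS III shift table by arm and visit for subjects with a baseline on the revised scale.
4. Show the 30 by arm with their observed Week 12 and Week 24 grades, both of which are on the revised scale.
5. Record in Section 14 any part of Protocol 8.6 that is still not produced, with the reason.

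The cost is some SAP wording and two or three tables from data already collected; the acuity and refraction changes are already derived. The downside is that mixed acuity charts and unconvertible Snellen entries need a footnote and a count of exclusions. Printing LogMAR to two decimals in the listing is an optional tidy-up. If the database is already locked, SAP Section 2 provides for added analyses to be documented in the study report.

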12.8. COVID-19 EXPOSURE AND VACCINATION DATA

The following COVID-19 exposure and vaccination information will be summarized. The number (%) of subjects will be presented:

- Number of vaccination doses received at the time of screening, Baseline, Week 12 and Week 24
- Documented COVID-19 prior to first dose and during the study

All data will be listed.

13. INTERIM ANALYSES

No interim analysis is planned.

An independently chaired Safety Review Committee (SRC) will review unblinded safety data at specified intervals for the duration of the study. The structure, function and operation of the SRC is detailed in the REN001-201 SRC charter. Reneo personnel and site Investigators and study teams will remain blinded for the duration of the study.

14. CHANGES FROM PLANNED ANALYSES SPECIFIED IN THE PROTOCOL

- The secondary endpoints have been updated following FDA advice. The PROMIS T-score has been promoted to a secondary endpoint and MFIS physical sub-scale score and PGIC (muscle symptoms) have been moved to exploratory endpoints. The order of testing of endpoints has also been updated to align with this change.
- As the PGIC is assessed at the end of study treatment (Week 24 or Early Termination) a while on treatment strategy was proposed in the protocol. However, with some subjects not completing their PGIC assessment until more than a week after their last dose of study medication the strategy has been changed. The primary analysis will include all recorded data, regardless of the duration between the subject's last dose of study medication and the assessment. Given some subjects will have been off treatment for more than 7 days before recording PGIC, this analysis will no longer be referred to as a 'while on treatment' strategy; instead, this is a 'treatment policy' strategy. Subjects with no PGIC assessment will be considered as missing unless the incidence of missing PGIC data exceeds 5%. If the incidence exceeds 5% a multiple imputation approach will be used. A 'while on treatment' strategy has also been included as a supplementary analysis, where only assessments within 7 days of the last dose of study treatment will be included.
- A responder endpoint has been defined for the PGIC muscle symptoms and PGIC fatigue symptoms in addition to the 7-point scale endpoints.
- Two additional exploratory endpoints based on the 12MWD have been defined to further support the primary analysis. The endpoints are the first and last 6-minute periods of the 12MWD and aim to investigate whether there is a difference in treatment effect in these two periods.
- The supplementary analysis for the primary endpoint using a while on treatment strategy has been updated to an ANCOVA following review comments from the FDA. The original while on treatment analysis proposed in the protocol is now referred to as a treatment period restricted analysis.
- Added the exploratory endpoint for the phenotypic description questions (exercise tolerance, gait stability and myopathy) which are asked at Baseline and Week 24.

APPENDIX 1 – SAS® CODE

Primary Endpoint Analyses

1: Repeated measures mixed model analysis (MMRM).

```
proc mixed data=<dataset>;  
  class treatment(ref='Placebo') visit subject mutation(ref='Other');  
  model chg=mutation baseline treatment visit treatment*visit / ddfm=kr  
    solution;  
  repeated visit / subject=subject type=un group=treatment;  
  lsmeans treatment*visit / cl diff;  
  estimate 'REN001 - Placebo: W24' treatment 1 -1 trt*visit 0 1 0 -1/cl;  
  estimate 'REN001 - Placebo: W12' treatment 1 -1 trt*visit 1 0 -1 0/cl;  
run;
```

Assumptions:

- treatment is 2 levels e.g. 1=REN001; 2=Placebo
- visit is 2 levels e.g. 1=Week 12; 2=Week 24
- mutation is 2 levels e.g. 1=m.3243>G; 2=Other
- chg is change from baseline; baseline is baseline score
- An unstructured covariance matrix is specified using type=un. If this analysis fails to converge, then an ANCOVA approach will be used instead.

2: Non-monotone multiple imputation.

```
proc mi data=<dataset> seed=<seednumber> nimpute=25  
  out=<outmidataset1> minimum=(. 0 0 0 0);  
  by treatment;  
  var mutation scrn bl w12 w24;  
  mcmc impute=monotone chain=multiple nbiter=200 niter=100;  
run;
```

Assumptions:

- Dataset has one record per subject in a horizontal structure for observed values at each visit
- Observed values for endpoint at each visit are contained in the variables - scrn=screening, bl=baseline, w12=week 12, w24=week 24
- If a subject has a missing baseline (either not collected or out of window) then the screening value will be used as baseline. However, for the multiple imputation model the time the data was collected will be preserved so the *scrn* variable will be the screening value and the *bl* variable will be missing and imputed. The imputed baseline values will only be used to facilitate the imputation of later visits but will not be used in the analyses.
- mutation is 2 levels e.g. 1=m.3243>G; 2=Other
- treatment is 2 levels e.g. 1=REN001; 2=Placebo

3: Monotone multiple imputation.

```
proc mi data=<outmidataset1> seed=<seednumber> nimpute=1  
    out=<outmidataset2> minimum=(. 0 0 0 0);  
by treatment _imputation_;  
var mutation scrn bl w12 w24;  
monotone reg;  
run;
```

Assumptions:

- Dataset is the output dataset from the non-montone MI step, and already contains the 25 imputations for each subject denoted in the dataset by the variable `_imputation_`
- Observed values for endpoint at each visit are contained in the variables - `scrn`=screening, `bl`=baseline, `w12`=week 12, `w24`=week 24
- If a subject has a missing baseline (either not collected or out of window) then the screening value will be used as baseline. However, for the multiple imputation model the time the data was collected will be preserved so the `scrn` variable will be the screening value and the `bl` variable will be missing and imputed. The imputed baseline values will only be used to facilitate the imputation of later visits but will not be used in the analyses.
- mutation is 2 levels e.g. 1=m.3243>G; 2=Other
- treatment is 2 levels e.g. 1=REN001; 2=Placebo

4: Combining multiple imputation analyses using MIANALYZE.

```
ODS OUTPUT PARAMETERESTIMATES=<outestdataset>;  
proc mianalyze data=<diffsdataset>;  
by visit;  
modeleffects estimate;  
stderr stderr;  
run;
```

Assumptions:

- Convert the resulting MI dataset to a vertical structure and analyse using MMRM (SAS code point 1) by imputation. Output the dataset of estimates (ODS OUTPUT DIFFS=<diffsdataset>;) keeping the visit comparisons of interest. Use this dataset in the MIANALYZE procedure.

Secondary Endpoint Analyses

5: PROMIS T-score - Repeated measures mixed model analysis (MMRM).

```
proc mixed data=<dataset>;  
  class treatment(ref='Placebo') visit subject mutation(ref='Other');  
  model chg=mutation base12mwd baseline treatment visit treatment*visit /  
        ddfm=kr solution;  
  repeated visit / subject=subject type=un group=treatment;  
  lsmeans treatment*visit / cl diff;  
  estimate 'REN001 - Placebo: W4' treatment 1 -1 treatment*visit 1 0 0 0 -  
1 0 0 0/cl;  
  estimate 'REN001 - Placebo: W12' treatment 1 -1 treatment*visit 0 1 0 0  
0 -1 0 0/cl;  
  estimate 'REN001 - Placebo: W18' treatment 1 -1 treatment*visit 0 0 1 0  
0 0 -1 0/cl;  
  estimate 'REN001 - Placebo: W24' treatment 1 -1 treatment*visit 0 0 0 1  
0 0 0 -1/cl;  
run;
```

Assumptions:

- treatment is 2 levels e.g. 1=REN001; 2=Placebo
- visit is 4 levels e.g. 1=Week 4; 2=Week 12; 3=Week 18; 4=Week 24
- mutation is 2 levels e.g. 1=m.3243>G; 2=Other
- chg is change from baseline; baseline is baseline score
- base12mwd is the Baseline 12MWD
- An unstructured covariance matrix is specified using type=un. If this analysis fails to converge, then an ANCOVA approach will be used instead.

Exploratory Endpoint Analyses

6: PGIC - ANCOVA.

```
proc mixed data=<dataset>;  
  class treatment mutation(ref='Other');  
  model pgic=mutation base12mwd treatment / ddfm=kr solution;  
  lsmeans treatment / cl diff;  
  estimate 'REN001 - Placebo' treatment 1 -1/cl;  
run;
```

Assumptions:

- treatment is 2 levels e.g. 1=REN001; 2=Placebo
- mutation is 2 levels e.g. 1=m.3243>G; 2=Other
- pgic is the numeric score
- base12mwd is the Baseline 12MWD

7: PGIC – Logistic regression.

```
proc logistic data=<dataset>;  
  class treatment mutation/param=glm;  
  model pgic=mutation base12mwd treatment/expb;  
  lsmeans treatment / cl exp diff;  
  estimate 'REN001 - Placebo' treatment 1 -1/exp cl;  
run;
```

Assumptions:

- treatment is 2 levels e.g. 1=REN001; 2=Placebo
- mutation is 2 levels e.g. 1=m.3243>G; 2=Other
- pgic is 2 levels responder endpoint e.g. 1=yes; 2=no
- base12mwd is the Baseline 12MWD

8: PGIC – monotone multiple imputation.

```
proc mi data=<dataset> seed=<seednumber> out==<outmidataset1> nimpute=25;  
  by treatment;  
  class pgic mutation;  
  monotone logistic(pgic=mutation base12mwd / details);  
  var mutation base12mwd pgic;  
run;
```

Assumptions:

- Dataset has one record per subject in a horizontal structure
- pgic is the numeric ordinal score (range of -3 to 3)
- mutation is 2 levels e.g. 1=m.3243>G; 2=Other
- treatment is 2 levels e.g. 1=REN001; 2=Placebo
- base12mwd is the Baseline 12MWD

